### **Statistical Analysis Plan**

The sample size calculation was based on a previous study [1] where the minimum clinically important difference in subjects was estimated to be at least 2 points on the Numeric Pain Rating Scale (NPRS) [2,3]. In this study, the sample size was calculated using the G\*Power 3.1.9 [4] program, with an estimated standard deviation of 1.08, a large effect size (0.8) [5], a statistical power of 95% (probability of type 1 error  $\beta$ ) and  $\alpha$  of 0.05. The study will require 84 participants. However, an additional 20% of participants will be added for possible sample loss, totaling 102 participants.

All dropouts during the study will be monitored, and the respective reasons for withdrawal will be recorded. All randomized participants will be included in the analysis regardless of whether they complete the intervention or not (where we will use intention-to-treat principles).

A descriptive statistic will be used to present the sociodemographic data and clinical characteristics of the participants. The Kolmogorov-Smirnov test will be utilized to test the normality of the data. For continuous variables with normal distribution (parametric), they will be presented as means and standard deviations, and for non-normal distribution (non-parametric), they will be presented as medians and interquartile ranges. Inferential statistical analysis will be conducted according to the intention-to-treat principle.

An analysis of variance (ANOVA) will be used to examine the effect of treatment, time (pre and post-treatment, 3 and 6 months follow-up), and the interaction between groups (GAG and CG) versus time. If differences between groups are identified, Tukey's multiple comparison test will be performed. For parametric data, paired t-test will be used for within-group comparisons (comparing baseline with follow-ups). The non-parametric statistical test, Wilcoxon's t-test, will be used if the data are not normally distributed. All statistical analyses will be performed using SPSS (IBM Co, Armonk, New York, USA) for Windows, V.19.0. The confidence interval will be set at 95%, and the significance

level will be defined at 5%. Additionally, to verify the magnitude of differences between interventions, the effect size (Cohen's d) will be calculated [7].

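### The sample size inputs (2 NPRS points, SD 1.08, effect size 0.8) do not agree: 84 follows from 0.8, which at SD 1.08 is 0.86 points, not 2

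*SAP*

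**What the plan says.** Everything is in the opening paragraph of the SAP, under the heading Statistical Analysis Plan. It begins "The sample size calculation was based on a previous study [1"], and continues that in this study "the minimum clinically important difference in subjects was estimated to be at least 2 points on the Numeric Pain Rating Scale (NPRS"). The next sentence lists what was entered in G*Power: "with an estimated standard deviation of 1.08, a large effect size (0.8) [5], a statistical power of 95" per cent, and alpha 0.05. The result is "The study will require 84 participants", raised to 102 for possible loss.

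The 2 points and the 0.8 carry different citations. The paragraph does not say how the 2 points, the SD and the 0.8 relate, whether 1.08 is the SD of scores or of change, whether the test is two-sided, or what the allocation ratio is. It never states outright that the 95% power is for 2 points.

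**The concern.** A standardised mean difference is the difference in points divided by the SD, so any two of these quantities fix the third. The paragraph offers all three as the basis of one calculation, and they do not fit together.

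This is the SAP's only statement of what the trial is designed to detect. If the pain result is null, a reader will turn to the 95% to judge whether a worthwhile effect could have been missed. As written, that reader cannot tell whether it refers to 0.86 points, to 2 points, or to some other difference on an SD that is not given.

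**Working it through.** **Inputs from the SAP's sample size paragraph:** difference 2 points; SD 1.08; d = 0.8; power 95%; alpha 0.05; total 84.

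**Assumed, because not stated:** two-sided test and 1:1 allocation. They are inferred because they reproduce 84 exactly.

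**Method:** two-sample t-test with n per arm. Power is the probability that a noncentral t variable with 2n − 2 degrees of freedom and noncentrality d × √(n/2) exceeds the two-sided 5% critical value.

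**1. Reproducing the plan's 84 from d = 0.8**

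- n = 41 per arm: power 94.7%, just short.
- n = 42 per arm: noncentrality 0.8 × √21 = 3.67, power 95.2%. Total 2 × 42 = **84**.
- A one-sided test would need 35 per arm, total 70, which does not match.

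Of the three effect inputs, only 0.8 is needed to obtain 84.

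**2. Do the three inputs agree?**

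- 2 / 1.08 = 1.85, not 0.8.
- 0.8 × 1.08 = 0.864 points, which is 0.864 / 2 = 43% of 2 points.
- 2 / 0.8 = 2.5: two points equals d = 0.8 only if the SD is 2.5.

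**3. What 2 points and SD 1.08 would give (d = 1.85)**

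- n = 8 per arm: power 93.1%.
- n = 9 per arm: power 95.8%. Total **18**, not 84.
- At 42 per arm, power for 2 points exceeds 99.99%.

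**4. If 1.08 is the wrong input**

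The plan gives no other SD, so the values below are assumptions that show the range.

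| Assumed SD | d = 2/SD | Power of 84 for 2 points | Total for 95% power |
|---|---|---|---|
| 2.0 | 1.00 | 99.5% | 54 |
| 2.5 | 0.80 | 95.2% | 84 |
| 3.0 | 0.67 | 85.5% | 120 |

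With 42 per arm, power is exactly 95% at d = 0.796, so the break-even SD is 2 / 0.796 = 2.51. At SD 3.0 the chance of missing a true 2-point difference is 100% − 85.5% = 14.5%, against the nominal 5%.

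**The case against.** The strongest reply is that nothing was miscalculated. On this reading the 2 points is background on what matters to patients, 0.8 is the design effect, openly labelled as large and separately cited, and 1.08 is reported but not used. The 84 is then correct for its stated effect size and the fault is one of reporting. It is true that the paragraph does not claim 95% power for 2 points and that 0.8 is in plain view. But the plan says that the calculation rests on the study from which it takes the 2 points, and it lists the SD among the G*Power inputs. Even if the 2 points is set aside, the design effect at SD 1.08 is less than half of the only clinically important difference that the plan names, and the plan does not say so.

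A second reply is that the harm is hypothetical. On the only SD given there is no shortfall, and SD 3.0 appears nowhere in the document. That stands: no loss of power has been shown. It is also fair that 102 are to be recruited. If all 102 gave data (51 per arm), power for 2 points at SD 3.0 would be 91.5% and the break-even SD about 2.77. That softens the figures, but 91.5% is still below 95%, and the plan attaches its 95% to 84.

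Third, these powers are for a single two-group t-test, whereas the SAP plans ANOVA over time and generalised estimating equations. This limits how literally any of the power figures can be read, the plan's own 95% included. It does not reconcile the inputs. A null result would also be read from its confidence interval, but that does not excuse a power statement whose target is unclear.

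**Conclusion.** The concern holds. That the inputs disagree is plain arithmetic and needs no assumption: 2/1.08 is 1.85, and 0.8 at SD 1.08 is 0.86 points. That 84 comes from 0.8 rests on a two-sided test and 1:1 allocation, both inferred from the exact match.

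The document does not show which input is wrong. If 1.08 is the SD of the analysed outcome, the trial has ample power for 2 points and the fault lies in the stated rationale. If it is not, the claim of 95% power for 2 points is unsupported until an SD is sourced, and fails at 84 if that SD exceeds about 2.51. The point should be fixed, because the stated sample size and power rest on these figures, but it does not show that the trial is underpowered.

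**What to change.** Keep 84 and 102. The sponsor should first settle which input is wrong, and delete nothing until that is done. Then restate the difference in points, the SD (with its source, and whether it is for scores or change) and d so that they agree, with the resulting power of 84.

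- **A. If 1.08 is the SD of the analysed outcome:** remove 2 points as the basis of the calculation and write: *84 participants (42 per group) give 95% power for d = 0.8, i.e. 0.86 NPRS points at SD 1.08, and above 99.99% for 2 points.* The 2 points then serves only as a reference value.
- **B. If it is not:** keep 2 points as the basis, replace 1.08 with a sourced SD, restate d as 2 divided by that SD, and give the power of 84 for 2 points at that SD, even if it is not 95%. Do not obtain the SD by working back from 2/0.8 = 2.5, since that would only make the figures agree without evidence.

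In either case, state that the test is two-sided and the allocation 1:1, if that is what was used.

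The cost is SAP wording only. Under A the plan can no longer say that its size rests on a 2-point difference. Under B, if the sourced SD is above about 2.51, it must report power below 95% for 2 points at 84.
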